4.8. Safety Analyses

All safety analyses will be conducted on the Safety Population. The safety data will be presented in individual listings and summary tables. Descriptive statistics will be used to summarize the safety data by period and both by treatment group and overall. The denominator for calculating the percentages will be based on the number of subjects on each treatment arm (ENT-01 or placebo) and overall in the Safety Population. The summary for the ENT-01 arm during the Fixed Dose period will also be broken down to the fixed dose levels.

No formal hypothesis-testing analysis of safety data will be performed.

4.8.1 Extent of Exposure

The extent of exposure will be summarized by the number of tablets received and number of days on treatment during the Dose Adjustment period and Fixed Dose period.

4.8.2 Adverse Events

Adverse events (AEs) will be coded by system organ class (SOC) and preferred term (PT) according to the latest version of the Medical Dictionary for Regulatory Activities (MedDRA). The intensity/severity of AEs will be graded according to the latest NCI-CTCAE. Treatment-emergent AEs (TEAEs) are defined as any AE occurring or worsening on or after the first dose of study treatment. AEs that have a possible, probable or definite relationship to study drug will be defined to be related to the study drug while others will be defined as “not related”. AEs with the closest relationship to the study drug will be used for summary.

The following types of summaries will be provided:

- Overview of TEAEs
- TEAEs by SOC and PT
- TEAEs by SOC, PT, and Maximum CTCAE toxicity grade
- TEAEs by SOC, PT, and Maximum CTCAE toxicity grade ≥ 3
- TEAEs by SOC, PT, and closest relationship to study drug
- TEAEs by PT in decreasing frequency
- Drug-related TEAEs by SOC and PT
- Drug-related TEAEs by PT in decreasing frequency
- Serious TEAEs by SOC and PT
- TEAEs leading to study treatment discontinuation by SOC and PT
- TEAEs leading to dose interruption by SOC and PT

All adverse event summaries will be presented by the dose the subject was on at the time of the AE. Adverse event summaries will also be presented during the following time periods:

- Dose Escalation
- Fixed Dose
- Dose Escalation and Fixed Dose (Treatment Period)
- Single Blind Placebo

- Washout
- Entire Study

In these tabulations, if a subject experiences the same preferred term multiple times within a period, then the event will be counted only once within the period.

In tabulation by severity (i.e., CTCAE toxicity grade),

- For a given preferred term, only the most severe preferred term for each subject will be included.
- For a given system organ class, only the most severe system organ class for each subject will be included.

Similarly, in tabulation by relationship,

- For a given preferred term, the most closely related preferred term to the study drug for each subject will be included.
- For a given system organ class, the most closely related system organ class to the study drug for each subject will be included.

TEAEs, serious TEAEs, and AEs leading to discontinuation from the study treatment will be provided in separate data listings.

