8.8 Adverse Event Assessment and Recording

All adverse events, exacerbations of concomitant illnesses, or events known to be related to underlying disease processes or concomitant medications are to be recorded on the CRF throughout the study. If a pre-existing condition worsens on study, the date on which the exacerbation began should be recorded. Onset dates for study treatment-related adverse events must be on or after the date of initial study treatment use. The need to record an adverse event on the CRF is not dependent on whether the adverse event is associated with the use of the study medication. In order to avoid vague, ambiguous or colloquial expressions, the adverse event should be recorded in standard medical terminology.

Adverse event recording will include the date of onset, severity, duration, whether or not the study medication was discontinued, or its dosage changed because of the event, the treatment given and the outcome. The investigator must also assess whether the event was related to the study medication, concurrent drug therapy, underlying disease, a combination of these factors, or if it is unknown. Subjects with an adverse event should be carefully followed to determine outcome.

The investigator will use the National Cancer Institute (NCI) Common Terminology Criteria for Adverse Events (CTCAE) V.4.03 definitions to grade the severity of the event.

Grade 1: Mild; asymptomatic or mild symptoms; clinical or diagnostic observations only; intervention not indicated

Grade 2: Moderate; minimal, local, or non-invasive intervention indicated; limiting age-appropriate ADL

Grade 3: Severe or medically significant but not immediately life-threatening; hospitalization or prolongation of hospitalization indicated; disabling; limiting self-care ADL

Grade 4: Life-threatening consequences; urgent intervention indicated

Grade 5: Death

The relationship or association of the study medication in causing or contributing to the adverse event will be characterized as remote, possible or probable as defined below:

- **Not related:** Evidence indicates no plausible direct relationship to the study medication
- **Remote:** Suggests other conditions are reasonably likely to account for the event including concurrent illness, progression or expression of the disease state, or reaction to concurrent medication

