- **Possible:** Suggests that the association of the event with the study medication is unknown; however, the adverse event is not reasonably supported by other conditions
- **Probable:** Suggests that a reasonable temporal sequence of the event with medication administration exists and, based upon the investigator's clinical experience, the association of the event with study medication seems likely
- **Definite:** Suggests that based upon the investigator's experience, the association of the event with the study medication seems very certain.

Procedures such as surgery should not be recorded as adverse events. However, the medical condition for which the procedure was performed should be reported if it meets the definition of adverse event.

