12.1 Data Management

All data relating to study procedures will be entered on to electronic CRFs provided by the sponsor. All forms must be completed electronically. All requested information must be entered on the electronic CRF. If an item is not available or not applicable this fact should be indicated by the use of "NA". Spaces should not be left blank. Electronic CRF will be reviewed during the monitoring visits. Data will be entered into a database. Data entry and management and the production of the clinical study report will be the responsibility of the sponsor or a designated agent.

The data cut-off for the study will be 60 days after entry of the last subject. If subjects remain on study thereafter, a revised final study report will be issued after the last subject has completed the final study evaluation.

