12.2 Data Capture and Management

The sponsor will provide the study sites with an electronic case report system.

Electronic CRFs will be completed for each subject. It is the Investigator's responsibility to ensure the accuracy, completeness, and timeliness of the data entered in each subject's eCRF. Source documentation supporting the eCRF data should indicate the subject's participation in the study and document the dates and details of study procedures, adverse events, and subject status.

The Investigator, or designated representative, should complete the eCRF as soon as possible after information is collected, preferably on the same day that a subject is seen for an

examination, treatment, or any other study procedure. Any outstanding entries must be entered immediately after the final examination. An explanation should be given for all missing data.

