The primary and secondary efficacy endpoints will be summarized by the subgroups based on the baseline CSBM rate (i.e., 0 - 0.9 or 1.0 – 3.0). Additionally, the primary and secondary endpoints will be presented by first and second “cohort” (i.e., the 1st cohort of subjects enrolled under the first part via the 3:1 randomization scheme; and the 2nd cohort of subjects randomized via the 1:1 randomization scheme).

Withdrawals, Dropouts, Loss to Follow-up

Subjects who withdrew from the study were not to be replaced.

Missing, Unused, and Spurious Data

When deriving endpoints that use dates, for dates that include missing values, the following conventions will be used.

Value	Imputation
Missing day, month, and year	Not imputed
Missing day and month	Day imputed to June 30th
Missing day	Day imputed to the 15th

When using dates from drug administration pages for the purposes of deriving treatment exposure, the following conventions will apply:

- If the start date is missing, it will be assumed that the first drug intake was given at the date of randomization. This date will replace all first administration missing dates.
- If the last administration date is missing, the date will be imputed with the date taken from the “Status of the Patient at the End of the Treatment” eCRF page (Date of last treatment) or if missing, with the date of last contact taken from the “Status of the Patient” eCRF page.

For missing or partial missing onset dates for adverse events, the following conventions will apply:

The start dates for AEs are important for the following:

1. Treatment-emergent adverse event (TEAE) algorithm. A TEAE is an event that first occurred or worsened in severity after baseline.
2. Designation of unique AE occurrences.
3. Completely missing or partially missing AE onset dates will be imputed after due diligence to obtain accurate AE information has failed. The imputation will consider the start and stop dates relative to each other, and relative to the date of consent and date of first dose.

AEs with start dates that are completely or partially missing will be analyzed as follows:

- If the start date of an event is completely missing, then the event is assumed to be treatment-emergent.
- If the start date has the month and year but day is missing, the event will be considered treatment-emergent if the month and year of the start date of the event are equal to, or greater than, the month and year of the date of first dose of study drug.

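### The catch-all in SAP 4.8.2 sends adverse events with unknown, NA or missing causality to 'not related', and so out of the two drug-related tables

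*SAP*

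**What the plan says.** SAP 4.8.2 turns the investigator's causality assessment into a two-way split. The operative words are "possible, probable or definite relationship to study drug will be defined to be related to the study drug while others will be defined as", and the label that completes them is 'not related'. Two planned outputs depend directly on the split: "Drug-related TEAEs by SOC and PT", and the companion table by preferred term in decreasing frequency. The same section plans a table by closest relationship to study drug.

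Protocol 8.8 describes the assessment in two steps. The investigator first considers possible causes: study medication, concurrent therapy, "underlying disease, a combination of these factors, or if it is unknown". A relationship scale follows with five levels: not related, remote, possible, probable and definite. The sentence introducing the scale names only three of the five.

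On incomplete entries, Protocol 12.1 says "If an item is not available or not applicable this fact should be indicated by the use of" NA, and that spaces should not be left blank. Protocol 12.2 adds: "An explanation should be given for all missing data".

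SAP 4.2 gives detailed conventions for missing dates. Its general methods provide a missing-data category when categorical variables are tabulated. Neither document has an analysis rule specific to unknown, NA or missing causality.

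**The concern.** The SAP names the three levels that count as related and leaves everything else to a residual class. Only two of the possible contents of that class, *not related* and *remote*, are judgements against the drug. An unknown, an NA or a blank is the absence of a judgement, yet the literal rule reports it as a negative one.

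The rule works in one direction: it can only take events out of the drug-related tables. Safety is a primary objective, and SAP 4.8 plans no hypothesis tests on safety data, so the descriptive tables are the safety result. A drug-related table that silently leaves out unassessed events understates what cannot be ruled out, and its reader has no means of seeing how many events were treated this way.

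**Working it through.** The plan states no figure on this point and no arithmetic applies. The check sets the provisions side by side.

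**Step 1: what can be recorded, and where the literal rule puts it.**

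| Recorded causality | Source | Class under SAP 4.8.2 read literally |
|---|---|---|
| Definite, probable, possible | Protocol 8.8 scale | Related |
| Remote, not related | Protocol 8.8 scale | Not related (a judgement was made) |
| Unknown | Protocol 8.8, causes sentence | Not related (no judgement) |
| NA | Protocol 12.1, general rule | Not related (no judgement) |
| Missing | Foreseen in general by Protocol 12.2 | Not related (no judgement) |

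Placing *remote* with *not related* is an explicit choice and is not at issue. The last three rows are.

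**Step 2: does another provision override this?**

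- The missing-data conventions in SAP 4.2 deal with dates only. One resolves doubt towards counting the event: "If the start date of an event is completely missing, then the event is assumed to be treatment-emergent". That rule decides timing, not cause, so it does not bind the causality default. It does show that the SAP settled the equivalent question for dates and left it open for causality.
- The missing-data category in SAP 4.2 would naturally apply to the table by closest relationship, which has causality as a column. It does not govern the two drug-related tables, where an event is either in or out. It is also unclear whether an entered unknown or NA counts as missing for that purpose.
- Protocol 9.2.2 plans summaries of AEs related to study medication and gives no rule for unassessed ones.

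Nothing overrides the literal reading for the two tables.

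**Step 3: what the rule does to a count.** For one preferred term in one arm and period, let *r* be the number of subjects with at least one record assessed possible or higher. Let *u* be the number with at least one unassessed record and none assessed possible or higher. SAP 4.8.2 counts a subject once per term and uses the closest relationship, so a subject with any related record of that term stays in *r*. The number of subjects with a drug-related event, had every record been assessed, lies between *r* and *r + u*. The literal rule always reports *r*, the lower limit, and does not show *u*. The error in that arm's count is therefore between 0 and *u* subjects, always downwards. The effect on the difference between arms depends on how *u* is split and could go either way.

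**Step 4: can *u* be sized?** No. Neither document gives a count or rate of events with unknown, NA or missing causality.

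**The case against.** The best case for the SAP is that its residual class has an obvious meaning. The protocol scale has five levels, the SAP names three, and the others are the remaining two. On that reading the SAP is merely silent on unassessed events. The reading is reasonable, but the sentence does not say it, and a programmer following the text would send every remaining value to 'not related'. Silence would need the same repair.

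The limits on size carry more weight, and they stand:

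- The investigator must assess relationship under Protocol 8.8, and blanks are discouraged under 12.1. The NA rule is general and not written for causality.
- 'Unknown' appears in the sentence about causes, not among the five levels. Whether the case report form offers it as a relationship response cannot be seen.
- Protocol 8.10 requires a causality assessment with each serious-event report, so gaps there should be rarest.
- Affected events remain in the all-causality, grade, serious and discontinuation tables, and TEAEs are listed.

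Counting unassessed events as related is a convention, and a separate category alone would be another defensible one. The fix uses both.

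Three stronger readings are tempting and are not supported:

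- *That the SAP contradicts the protocol's definition of possible.* The definition begins "Suggests that the association of the event with the study medication is unknown", but goes on to require that other conditions do not reasonably explain the event. Unknown alone is therefore not possible, and an unknown association that is graded possible counts as related in the SAP.
- *That events attributed to a combination of factors are lost.* The combination concerns causes. The event still receives a level on the scale, which can be possible or higher.
- *That the rule could mask the trigger for the study-wide hold.* The hold applies when more than 2 subjects have a grade 4 or 5 event meeting the rule's own relatedness criterion (Protocol 3.1 and 8.15, SAP 2.3). Nothing ties that count to the grouping in SAP 4.8.2.

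**Conclusion.** The point holds as a minor defect of definition. Read literally, SAP 4.8.2 classes AEs with unknown, NA or missing causality as not related and removes them from the two drug-related TEAE tables. No other provision restores them there. The direction is anti-conservative for each arm's drug-related counts.

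The size cannot be estimated and is probably small. A reader might want to attach a percentage of records, or a number of subjects lost for a common event such as nausea. The documents give no rate to support either, and a percentage of records would not carry over to subjects, because a subject with one related record of a term stays in the count.

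The conclusion assumes that the catch-all is programmed as written and that some events still have no usable assessment after query. If every event receives one of the five levels, the rule changes nothing.

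**What to change.** In SAP 4.8.2, replace the residual class with a complete mapping:

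- *Not related*: AEs the investigator assessed as not related or remote.
- *Related*, for the two drug-related tables: TEAEs assessed as possible, probable or definite, and TEAEs whose relationship is still unknown, NA or missing after query.
- Footnote each drug-related table with the number of unassessed TEAEs by arm, so that a reader can see how far the table depends on the convention.
- In the table by closest relationship, show unassessed events as a separate category, in line with SAP 4.2. State where that category ranks when a subject has several records of one term. Above remote and below possible would agree with the rule above.

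The mapping should be checked against the responses the case report form actually offers, since the sentence introducing the scale in Protocol 8.8 and the five levels after it do not match.

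The cost is a few lines in the SAP and a footnote in the table shells. No new data are needed and the rule is the same in both arms. The downside is that drug-related percentages may be slightly higher in both arms.

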4.8.3 Deaths

All deaths and reasons for death will be provided in a listing.

4.8.4 Physical Examinations

Summaries of physical examinations will present frequency distribution of abnormal findings by body system and visit. The denominators for calculating the percentages will be based on the number of subjects evaluated for a particular body system. All physical examination findings will be presented in a data listing.

4.8.5 Laboratory Data

Clinical labs will be performed by a central laboratory. Labs to be drawn during the study include serum chemistries, a hematology panel, coagulation panel and urine analysis. Clinical laboratory values will be expressed using conventional units.

Descriptive statistics by period (or visit) and treatment group will be presented for each laboratory parameter. Changes from Baseline as well as shift tables will be presented. All laboratory values will be classified as normal, below normal, or above normal based on normal ranges supplied by the central laboratory. Frequencies of abnormal values and frequencies of clinically significant abnormal values will be presented in tabular form. In the event of repeat values, the last non-missing value per study period will be used.

All laboratory data will be provided in data listings.

4.8.6 Vital Signs

The actual value and change from baseline to each on study evaluation will be summarized for vital signs. By-subject listings of vital sign measurements will be presented in data listings.

4.8.7 Electrocardiogram

ECG results will be summarized descriptively, including the number and percent of subjects with normal, abnormal and clinically significant abnormal results at Baseline and each study visit. The denominators for calculating the percentages will be based on the number of subjects with non-missing values in each assessment.

All ECG data for each subject will be provided in data listings.

4.8.8 Columbia-Suicide Severity Rating Scale (C-SSRS)

The number and percentage of patients with Suicidal Ideation, Suicidal Behavior, and Self-Injurious Behavior without Suicidal Intent based on the Columbia-Suicide Severity Rating Scale (C-SSRS) during the treatment period will be summarized by treatment group. Treatment-emergent Suicidal Ideation, Suicidal Behavior, and Self-Injurious Behavior without Suicidal Intent will be based on Visit 3 through End of Study (EOS)/Early Termination (ET). In this summary, the number and percentage of patients who experience the particular event at least once during the treatment period will be summarized. The particular events are:

- Suicidal Ideation (1-5)
 1. Wish to be Dead
 2. Non-specific active suicidal thoughts
 3. Active suicidal ideation with any methods (not plan) without intent to act
 4. Active suicidal ideation with some intent to act, without specific plan
 5. Active suicidal ideation with specific plan and intent
- Suicidal Behavior (6-10)
 6. Preparatory acts or behavior
 7. Aborted attempt
 8. Interrupted attempt
 9. Non-fatal suicide attempt
 10. Completed suicide
- Self-injurious behavior without suicidal intent

For the composite endpoint of suicidal ideation (Categories 1-5), the number and percentage of patients who experience any one of the five suicidal events at least once during the treatment period will be summarized by treatment group. For the composite endpoint of suicidal behavior (Categories 6-10), the number and percentage of patients who experience any one of the five

suicidal behavior events at least once during the treatment period will be summarized by treatment group.

Two shift tabulations from baseline for the C-SSRS will be produced by treatment group during the treatment period. The Baseline C-SSRS assessment includes both (A) Lifetime Assessment (for both the suicidal behavior and for the suicidal ideation sections) and (B) Recent Assessment: 1 year prior to study start for the suicidal behavior section, and 1 month prior to the study start for the suicidal ideation section. A separate shift tabulation will be produced using each of these two baselines. The three groupings for the shift tables are: (a) No suicidal ideation or behavior, (b) Suicidal Ideation, and (c) Suicidal Behavior. Suicidal Ideation includes any one of the five suicidal ideation events (Categories 1-5). Suicidal behavior includes any one of the five suicidal behavior categories (Categories 6-10). Each patient is counted in one cell only for each of the two tabulations. Patients with both Suicidal Ideation and Suicidal Behavior are included in the Suicidal Behavior category for the particular tabulation.

Patient listings for the C-SSRS will also be produced.

